Blinding of trial staff: two members of staff were available at each site to run the study. Randomisation into the treatment or placebo arm of the study occurred at Visit 2, after all the documentation had been completed. At this point, the member of staff carrying out the PTNS or sham was unblinded. That same staff member carried out all 12 treatments for the patient. Following the final treatment the member of staff who remained blinded collected all of the final data, before allowing the patient to find out if they were in the sham or treatment arm. In this way, the staff member conducting the final meeting with the patient remained blinded until the end.

Sample size determination

Research into treatment of FI is currently hampered by the lack of a valid and reliable tool that allows standardisation of outcomes. There are advantages and disadvantages of the numerous possible quantitative outcome variables e.g. individual symptoms and composite scores, and generally poor correlation of either with disease specific or generic quality of life measures. Of possible outcomes, the most frequently used and

probably least affected by subjective reporting differences is number of FI episodes per unit time (usually per week). This outcome, obtained directly from the mean of 2 week bowel diary frequencies has been employed in almost all contemporary studies of FI interventions including recent SNS studies. The problem with this variable is that, being a count, it has a Poisson distribution and is over-dispersed i.e. has greater variability than expected. This raises major difficulties in defining a *clinically significant* mean reduction in FI episodes per week in a population of patients with widely dispersed starting FI frequencies. To counter this problem, almost all contemporary studies have adopted a primary outcome using a categorical measure of percentage reductions i.e. the proportion of patients who have a 50% or greater reduction in faecal incontinence episodes per week. We justify this approach on the following basis:

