Age, sex, history of faecal incontinence (including type), urinary symptom history, previous faecal incontinence treatments, medications, past medical history, past obstetric history. (see CRF 2 v5 for items)

Bowel diary (14 consecutive days)

Gastrointestinal quality of life index, patient centred FI symptoms, SF-36 Health Survey, QoL scale for faecal incontinence, St. Mark's faecal incontinence score, EQ-5D health questionnaire (see CRF 3 v3 for detail)

Follow up

Visits 2-13: PTNS or tens machine settings and response (sensory or motor), adverse events, any change in pad usage, any changes in medication use? (see CRF 5 v3)

Week 7: bowel diary over 7 consecutive days

Final visit (post treatment) (week 14): which treatment did patient think they were on?

Any effect on urinary symptoms? Any change in loperamide or codeine use? Any change in pad use? How patient felt before, during and after treatment, Likert scale of success.

Bowel diary over 14 consecutive days

CRF 3 v3

Timing of data collection

Event	Visit 1	Telephone Conversation	Visit 2	Visits 3-13	Visit 14
Eligibility assessment	X				
Bowel Diary		X		Visit 7-8	X
Consent			X		
Participant Contact Information Sheet			X		
Eligibility assessment (CRF1)			X		
Initial assessment (CRF2)			X		
Questionnaires (CRF3)			X		X
Randomisation			X		
Randomisation information (CRF4)			X		
Intervention			X	X	
Record stimulation parameters adverse events and medication / pad usage (CRF5)			X	X	
Adverse Events Log			X	X	X
Concomitant Medications Log			X	X	X
Post treatment Information (CRF6)					X
Final Study Visit Information (CRF7)					X

GENERAL ISSUES FOR STATISTICAL ANALYSIS

All analyses will be conducted two sided and significance interpreted at the 5% level.

Blinding of the statistical analysis

The trial statistician will remain blind to allocation until this analysis plan was signed off

Analysis populations

Intent-to-treat population

The intention-to-treat (ITT) sample is defined for this trial as all participants randomised into the trial, *who received at least their first treatment*, included in the intervention group to which they were randomised.

Available-case population

N/A

Per protocol population

Patients attending at least 10 treatment sessions in 13 weeks will be classed as treatment completers.

Safety population

N/A

Other populations

N/A

Database

Description

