All patients randomised who receive the first treatment will be included in the intention-to-treat analysis of primary endpoint. Prior to the first treatment, it was anticipated that some patients (up to 10%) would fail to attend after eligibility was assessed due to a failure of compliance with the travel and attendance needs of the treatment course or study. These were not counted as study recruits. Those in whom post-treatment data are unavailable at 14 weeks for any reason (loss to follow up, failure to complete treatment) will have their outcome multiply imputed under the assumption of missing at random (MAR) using variables prognostic of outcome, such as measure of outcome made at baseline, and others that are predictive of missingness such as mean number of FI episodes per week at baseline, age, sex, and where available, mid-study bowel diary data. See appendix (b) for details. Multilevel multiple imputation will be performed using the multivariate normal distribution in Realcom Impute, using treatment allocation, patient sex and allocation as auxiliary variables. After a burn in of 1,000 runs of the MCMC sampler, missing values will be filled every 500th run to create a total of 10 completed datasets for analysis. The data will be analysed in Stata and the results pooled by Rubin's rules.

Method for handling centre effects

Study centre will be included as a random effect

Method for handling randomisation stratification or minimisation factors

Patient sex will be included as a fixed effect, study centre as a random effect

Method for handling clustering effects

The intraclass correlation coefficients (ICC) and their 95% confidence intervals for the outcomes by centre (level 2) will be estimated using the user-contributed Stata command *sea_obi* which allows the ICC to be negative. Random effects models will be fitted by restricted maximum likelihood estimation (e.g. *xtmixed ...*, *reml*). However, should these fail due to the between centre variance being close to zero, random effects models will be fitted by generalised least squares (e.g. *xtregress*). If ICCs are estimated as ≤ 0 then we will use similar regression models without adjusting for clustering.

Method for selecting other variables that will be adjusted for

This was agreed by consensus prior to any data extraction and the decision was: fit fixed effects for sex, randomisation and baseline level of outcome.

Multiple comparisons and multiplicity

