No adjustments to p-values planned

Method for handling non-adherence

All patients randomised who receive the first treatment will be included in the intention-to-treat analysis of primary endpoint.

Method for handling time-varying interventions

N/A

Method for handling outliers and influential points

N/A

Data from external sources

N/A

Derived and computed variables

In the bowel diary, participant's record:

Controlled bowel motions: No incontinence – pads or pants remained clean

2. Uncontrolled bowel movements: Incontinence – underwear, pads or pants got dirty.

Within this section patients are asked how many of those times they:

a. Didn't make it in time to the toilet (rush)

b. Didn't feel the bowel movement until after it had happened (passive leakage)

The FI episodes will be calculated from those of 'Uncontrolled bowel Movements', whether this be 'rush' or 'passive leakage', by adding the two together.

DESCRIPTIVE ANALYSES

NB To help identify problems with missing data, outlying values, or other errors, full descriptive statistics **MUST** be produced for all variables in the database(s)

Participant flow

Participant throughput will be summarised in a CONSORT diagram.

Representativeness of sample

N/A

Baseline comparability of randomised groups

Demographics

Age and sex distributions will be described, by trial arm

Prior and concurrent medications

Proportion of patients taking loperamide and/or codeine

Baseline and screening conditions

Severity of FI symptoms according to bowel diary (i.e. mean number of episodes per week, recorded over a 14 day period)

Baseline medical history

Previous treatment for FI, and obstetric history. These are binary variables, except for number of previous vaginal deliveries (0, 1, 2, 3, 4, 5 or 6), and will be reported as number and percentage.

Baseline physical exam

N/A

Cluster characteristics if cluster randomised

N/A

Characteristics of care providers where applicable

N/A

Comparison of losses to follow-up

The proportion of patients withdrawing will be compared descriptively by arm

Comparison of compliance to treatment and protocol

The proportion of patients attending one or more treatment sessions will be compared descriptively.

The distribution of the proportion of treatment sessions attended per patient will be compared descriptively by arm. Participants who receive ≥ 10 treatments in 13 weeks will be considered to have received a full set of treatments for the per protocol analysis.

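### The set labelled intention-to-treat leaves out randomised patients who never start treatment, and no analysis of all randomised patients is planned

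*SAP*

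**What the plan says.** Under Analysis populations, the SAP begins with the usual definition, "The intention-to-treat (ITT) sample is defined for this trial as all participants randomised into the trial", and then limits it to those "who received at least their first treatment". The section on withdrawals, loss to follow-up and missing data applies the same limit to the primary endpoint: "All patients randomised who receive the first treatment will be included in the intention-to-treat analysis of primary endpoint". The section on non-adherence repeats that sentence.

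On timing, the blinding section says: "Randomisation into the treatment or placebo arm of the study occurred at Visit 2, after all the documentation had been completed". It continues: "At this point, the member of staff carrying out the PTNS or sham was unblinded". The data collection schedule places randomisation and the first intervention at Visit 2.

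On losses before treatment, the withdrawals section says that "it was anticipated that some patients (up to 10%) would fail to attend after eligibility was assessed", for reasons of travel and attendance, and adds: "These were not counted as study recruits". The sample size section describes the 10% allowance as failure to attend the second visit, which it identifies as the visit for allocation and first intervention.

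No wider set is defined. The available-case, safety and other populations are marked not applicable, as are supporting and sensitivity analyses of the primary outcome. The per protocol set, at least 10 sessions in 13 weeks, is narrower still.

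**The concern.** Intention-to-treat analysis keeps the comparison that randomisation created. A set that depends on something happening after randomisation no longer has that guarantee, however few patients are lost. Treated-only sets are easiest to defend when nobody involved in starting treatment knows the allocation. Here the person who delivers the first session does know it. The patient and the final assessor stay blinded, but neither of them delivers that session.

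Two things are at stake. The primary result would be reported as intention-to-treat when it is a modified set. And no planned analysis would show whether leaving out the non-starters mattered.

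**Working it through.** **Order of events, from the SAP's own sections**

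| Step | Where stated | Relation to allocation |
|---|---|---|
| Eligibility assessed; up to 10% then fail to attend visit 2 | Withdrawals section; Sample size determination | Before |
| Visit 2 documentation completed | Treatment masking | Before |
| Randomisation at visit 2; treating staff member unblinded | Treatment masking | At |
| First treatment at visit 2, which decides entry to the ITT set | Data collection schedule; Analysis populations | After |

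The 10% are lost at the first step and the restriction acts at the last, so the first cannot justify the second. The withdrawals section places the 10% loss before first treatment rather than before allocation. Read literally, that could let a randomised non-starter be treated as never recruited.

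**The plan's own figures.** Inputs from Sample size determination: 55% v 35%, two-sided 5%, 80% power, 1:1.
- Without continuity correction: n per arm = [1.960 × √(2 × 0.45 × 0.55) + 0.842 × √(0.55 × 0.45 + 0.35 × 0.65)]² / 0.20² = 95.9, so 96.
- With continuity correction: (95.9/4) × [1 + √(1 + 4/(95.9 × 0.20))]² = 105.7, so 106 per arm and 212 in total. This is the stated figure.
- Allowance: 212/0.9 = 235.6, against the stated 235.

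The 227 randomised already exceed 212, so analysing all of them needs no new sample size.

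**Possible size.** The SAP gives neither the number of non-starters nor the arm sizes. Assume 114 PTNS and 113 sham, with 62 and 40 responders, close to the planned rates. Assume also that every non-starter is a non-responder.
- Nobody dropped: 62/114 − 40/113 = 54.4% − 35.4% = 19.0 points.
- Five dropped per arm: 62/109 − 40/108 = 56.9% − 37.0% = 19.8 points, a shift of about 0.9 before rounding.
- Five dropped from PTNS only: 56.9% − 35.4% = 21.5 points, a shift of about 2.5.
- Five dropped from sham only: 54.4% − 37.0% = 17.4 points, a shift of about 1.6 the other way.

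**What the planned imputation would do.** It assumes MAR and has random allocation in the imputation model (appendix table). Non-starters would have baseline data only, so they would be imputed at roughly the rate of similar treated patients in their arm. Ignoring baseline differences, five PTNS non-starters give (62 + 5 × 0.569)/114 = 64.8/114 = 56.9%, the treated-only figure again. Counting them as non-responders gives 62/114 = 54.4%. Imputation therefore restores the analysis set but hardly moves the estimate. Only the second calculation shows how sensitive the result is to the non-starters.

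**The case against.** The best defence is that little can go wrong in practice. Allocation and first treatment fall within one visit, after the paperwork, so a randomised patient has little time in which to drop out. Patients are blinded. The restriction is stated openly as this trial's definition. The SAP plans a CONSORT diagram, withdrawals by arm and a description of attendance, so non-starters may well be visible. The clause may only have been meant to set visit-2 non-attenders apart from recruits.

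Most of this stands as a limit on size. It does not rescue the definition: stating a restriction openly does not make the set intention-to-treat, and a small count is also a reason not to need the restriction.

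Three stronger readings are tempting and are not supported:
- *The unblinded treater selects who is analysed.* No section gives that person discretion over whether treatment starts, and the only reasons the SAP gives for non-attendance are travel and attendance. It is a possible risk, not a documented one.
- *The attendance summary must be 100% by construction.* The SAP says "The proportion of patients attending one or more treatment sessions will be compared descriptively" and names no analysis set. Taken over all randomised patients, it would report the non-starters.
- *The 10% are the excluded group.* The sample size section places their loss before allocation.

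**Conclusion.** The point holds as a matter of definition and label. The only planned primary analysis uses a modified intention-to-treat set that depends on an event after randomisation and after the treater is unblinded, and no analysis of all randomised patients backs it up. It should be changed, because the change is nearly free and restores the randomised comparison.

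The effect on the result is unknown and probably small. With five non-responding non-starters, the assumed shift runs from about 0.9 points when both arms lose the same number to about 2.5 when all are in PTNS, against a planned 20. A reader might take 2.5 points as the expected bias, or as what imputation would correct. It is neither: it is a one-arm extreme on an assumed count, and imputation under MAR would leave the PTNS rate near 56.9%.

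**What to change.** - Define ITT, under Analysis populations and in the withdrawals and non-adherence sections, as all 227 randomised participants in the arm assigned. Handle missing outcomes by the multiple imputation already planned. Because documentation is completed before randomisation, non-starters should have the baseline data it needs.
- Keep the treated-only set as a supportive analysis labelled modified ITT.
- Replace the not-applicable entry for sensitivity analyses of the primary outcome with one that counts non-starters in both arms as non-responders.
- Report the number randomised but not treated, by arm, in the planned CONSORT diagram, and state that the attendance summary covers all randomised patients.
- Align the withdrawals section with the sample size section, so that the 10% are clearly patients lost before allocation.
- Record the change with its date in the SAP's amendments section.

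The cost is wording in a few sections, one short extra model run and probably only a few more imputed outcomes. No sample size or data collection changes.

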replace FI1_rev=2 if FI1==4
replace FI1_rev=3 if FI1==3
replace FI1_rev=4 if FI1==2
replace FI1_rev=5 if FI1==1

egen FIQoL_lif = rowmean(FI2a FI2b FI2c FI2d FI2e FI2g FI2h FI3b FI3l
FI3m)
egen FIQoL_cop = rowmean(FI2f FI2i FI2j FI2k FI2m FI3c FI3h FI3j
FI3n)
egen FIQoL_dep = rowmean(FI1_rev FI3d FI3f FI3g FI3i FI3k FI4)
egen FIQoL_emb = rowmean(FI2l FI3a FI3e)

egen mFIQoL_lif = rowmiss(FI2a FI2b FI2c FI2d FI2e FI2g FI2h FI3b
FI3l FI3m)
egen mFIQoL_cop = rowmiss(FI2f FI2i FI2j FI2k FI2m FI3c FI3h FI3j
FI3n)
egen mFIQoL_dep = rowmiss(FI1_rev FI3d FI3f FI3g FI3i FI3k FI4)
egen mFIQoL_emb = rowmiss(FI2l FI3a FI3e)

replace FIQoL_lif =. if mFIQoL_lif ~= 0
replace FIQoL_cop =. if mFIQoL_cop ~= 0

```

```
replace FIQoL_dep =. if mFIQoL_dep ~= 0
replace FIQoL_emb =. if mFIQoL_emb ~= 0
```

Variables to be used in the multilevel multiple imputation

Outcomes that are reported as a group of domains will be imputed together where possible. Baseline measures, mid-treatment (bowel diary data only) and end of treatment outcomes will be included together in the multivariate response. Centre is the only level 2 variable (random intercepts)

Outcomes	Imputation Variables	
	To include in multivariate response	Auxillary variables
Mean number of FI episodes per week	Mean number of FI episodes per week, St Mark's Continence Score, Likert	Age, Sex and random allocation
GI QOL Index (reported as total score)	Mean number of FI episodes per week, St Mark's Continence Score, GI QOL	Age, Sex and random allocation
Patient centered outcomes form	Patient centered outcomes form	Age, Sex and random allocation
SF-36 (eight domains)	SF-36 (4 domains at a time)	Age, Sex and random allocation
Quality of life scale for FI (four domains)	QOL for FI	Age, Sex and random allocation
St Marks Continence Score	Mean number of FI episodes per week, St Mark's Continence Score	Age, Sex and random allocation
EQ-5D	EQ-5D	Age, Sex and random allocation

List of case report forms (see statistics master file for detail)

- CRF 1 – Eligibility assessment
- CRF 2 – Initial assessment
- CRF 3 – PRE-TREATMENT questionnaires
- CRF 3 – POST-TREATMENT questionnaires
- CRF 4 – Randomisation
- CRF 5 – Record stimulation parameters adverse events and medication / pad usage
- CRF 6 – Post-treatment information
- CRF 7 – Final study visit information
- BOWEL DIARY – PRE-TREATMENT (14 days)
- BOWEL DIARY – MID-TREATMENT (7 days)
- BOWEL DIARY – POST-TREATMENT (14 days)

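### Four rows of the SAP's imputation table omit FI episodes and the mid-study diary, which its missing-data section names as predictors of missingness

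*SAP*

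**What the plan says.** In the SAP section on methods for withdrawals, loss to follow-up and missing data, patients without post-treatment data "will have their outcome multiply imputed under the assumption of missing at random (MAR"). The imputation is to use the baseline measure of the outcome and other variables "predictive of missingness such as mean number of FI episodes per week at baseline, age, sex, and where available, mid-study bowel diary data". The section then points onward: "See appendix (b) for details".

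That appendix, on the variables for the multilevel multiple imputation, opens with two general rules. The first is "Outcomes that are reported as a group of domains will be imputed together where possible". The second is "Baseline measures, mid-treatment (bowel diary data only) and end of treatment outcomes will be included together in the multivariate response". A table then lists, outcome by outcome, what enters the multivariate response:

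- FI episodes are written into three rows: FI episodes, GI QOL and St Mark's.
- Four rows name only the instrument itself: patient-centred outcomes ("Patient centered outcomes form"), SF-36 ("SF-36 (4 domains at a time"), FI-QOL and EQ-5D.
- Every row has age, sex and allocation as auxiliary variables.

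The mid-study data come from one source, given under Follow up: "Week 7: bowel diary over 7 consecutive days". The Timing of data collection table places the questionnaires (CRF3) at visits 2 and 14 only.

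**The concern.** MAR is an assumption about the variables conditioned on. The SAP names four predictors of missingness, and two of them, baseline FI and the mid-study diary, are absent from the four rows. The SAP gives no reason. FI-QOL, an instrument specific to faecal incontinence, is imputed without FI episodes, while the gastrointestinal index is imputed with them.

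The questionnaires are not repeated mid-treatment, so a row without FI episodes holds no information from the treatment period. The secondary analysis models already contain allocation, the outcome's baseline value, sex and centre. For EQ-5D the imputation model adds only age to that set, so for patients missing the week-14 score it offers little beyond a complete-case ANCOVA. The SAP plans no sensitivity analysis for the secondary outcomes that might show the difference.

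The outcomes concerned number 8 (SF-36 domains) + 4 (FI-QOL domains) + 1 (EQ-5D) + 1 (patient-centred score) = 14. If patients leave because their incontinence is not improving, and do so differently by arm, the treatment difference in these outcomes is biased although the data that would reduce the bias have been collected.

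**Working it through.** **Text against table.** No figure in the SAP bears on this point, so the first step is a comparison.

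| Named as predictor of missingness | In the FI, GI QOL and St Mark's rows | In the patient-centred, SF-36, FI-QOL and EQ-5D rows |
|---|---|---|
| Baseline FI episodes | yes | no |
| Age | yes | yes |
| Sex | yes | yes |
| Mid-study diary | yes, through FI episodes | no |

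**Size of the possible bias.** The SAP gives no correlations and no dropout rates after the first treatment, so every input here is an assumption:

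- 400,000 simulated patients per scenario, randomised 1:1, with standardised variables and higher scores worse.
- Correlation 0.6 between baseline and final score, and 0.6 between baseline and mid-study FI.
- Correlation r = 0.3 or 0.5 between mid-study FI and final score; all remaining correlations 0.3.
- Treatment lowers mid-study FI by 0.3 SD and the final score by r × 0.3, that is 0.3 × 0.3 = 0.09 SD or 0.5 × 0.3 = 0.15 SD.
- Probability that the final score is missing = 1/(1 + exp(−(m + s × mid-study FI))), with m set to give 5%, 12% or 20% missing overall.
- Three patterns for the log-odds slope s per SD: 0.7 in both arms; 0 in PTNS and 0.7 in sham; −0.7 in PTNS and 0.7 in sham.
- Missing final scores are filled by regression, and the arms are compared by ANCOVA on the baseline score. Bias = effect after imputation − effect with complete data.

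Bias (SD) when the imputation model leaves FI out, as in the four rows:

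| Missing | r | Equal in both arms | Sham only | Opposite directions |
|---|---|---|---|---|
| 5% | 0.3 | 0.002 | 0.004 | 0.008 |
| 5% | 0.5 | 0.002 | 0.012 | 0.022 |
| 12% | 0.3 | 0.001 | 0.010 | 0.021 |
| 12% | 0.5 | 0.004 | 0.027 | 0.051 |
| 20% | 0.3 | 0.004 | 0.015 | 0.030 |
| 20% | 0.5 | 0.009 | 0.043 | 0.084 |

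In these patterns the bias shrinks the apparent benefit. Reversing the dropout pattern would reverse the sign. Adding baseline FI alone removes only part of it: at 20% missing and r = 0.5, 0.043 falls to 0.033 and 0.084 to 0.067. Adding the mid-study diary as well brings the bias to 0.002 SD or less in absolute value in every scenario.

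**Against sampling error.** With the SAP's target of 106 per arm, the standard error of a difference in SD units is √(2/106) = 0.137. With a baseline correlation of 0.6 it is 0.137 × √(1 − 0.6²) = 0.110. The largest bias in each column is then 0.009/0.110 = 0.08, 0.043/0.110 = 0.39 and 0.084/0.110 = 0.76 of a standard error.

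**If some diaries are missing.** The runs above give every dropout a mid-study diary. In a separate simulated case with 10% missing and half the dropouts without a diary, the true effect was 0.313, the model as tabulated gave 0.286, and the model with FI added gave 0.299. The share of bias removed is (0.299 − 0.286)/(0.313 − 0.286) = 0.013/0.027, about half.

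**The case against.** The missing-data paragraph opens with the primary endpoint, gives its predictors only as examples, and hands the detail to the appendix. For FI episodes the appendix delivers what the paragraph describes. The appendix sentence on mid-treatment data is not limited to particular rows and might be meant for all of them. Choosing auxiliary variables is partly a matter of judgement, and splitting SF-36 into groups of four suggests that model size was already a constraint.

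Part of this stands. The conflict is a mismatch, not a flat contradiction, and the list is illustrative. But the appendix that the paragraph defers to covers the secondary outcomes, and its table writes FI episodes into some rows and not others, which tells against the reading that the diary enters every model. If that reading were intended, the table would still need correcting. Model size explains little for EQ-5D or the patient-centred form.

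Three stronger conclusions are tempting, and the SAP supports none of them:

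- A reader might infer that the four models lack the data that explain withdrawal. They do contain age and sex, both named as predictors, and the instrument's baseline score. Nothing in the SAP shows that mid-study FI drives withdrawal.
- A reader might infer that the diary is the only measurement after baseline in a patient who leaves late. Changes in pad and medication use are also recorded at visits 2 to 13. The diary is only the one mid-treatment measure that the appendix uses.
- A reader might infer that the secondary results are materially biased. That needs FI-driven dropout that differs between arms, and even the largest simulated bias is below one standard error.

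**Conclusion.** The mismatch is real and confined to secondary outcomes. Four of the seven imputation rows, covering 14 modelled outcomes, omit baseline FI and the mid-study diary although the SAP's own text names both as predictors of missingness. The primary outcome is not affected: it is computed from FI episodes, whose row holds baseline, mid-study and final values, and none of the four rows feeds it.

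The bias is negligible (under 0.01 SD) if dropout depends on FI equally in both arms. It is roughly 0.00 to 0.08 SD if that dependence differs by arm, with the upper end needing 20% missing, r = 0.5 and dropout that runs in opposite directions in the two arms. These figures rest wholly on assumed inputs. Confidence is high about what the table contains and low about the size of any bias. The change deserves to be made because it is cheap and makes the MAR assumption more credible, not because harm to the results has been shown.

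**What to change.** In the appendix table, add weekly FI episodes to the multivariate response of the patient-centred, SF-36, FI-QOL and EQ-5D rows: baseline and mid-study values, and the end-of-treatment value where the model allows. This agrees with the missing-data section and with the GI QOL and St Mark's rows. If the omission was deliberate, give the reason and amend the missing-data section instead. The SAP's amendments section records that this listing was updated during analysis, so the change should be logged as an amendment.

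The cost is modest and needs no new data. Each SF-36 block and the FI-QOL model would grow from 4 × 2 = 8 responses to 8 + 3 = 11. EQ-5D and a single patient-centred score would grow from 2 to 5. The added variable is an over-dispersed count in a multivariate normal model with centre random intercepts. If the SF-36 or FI-QOL models do not converge, fit fewer domains at a time. Patients who leave before week 7 have no mid-study diary, so for them only baseline FI helps.

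### No visible imputation model includes treatment received, though the SAP names stopping treatment as a cause of missing outcomes; PTNS response can be overstated if early stoppers do worse

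*SAP*

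**What the plan says.** The SAP section on withdrawals, loss to follow-up and missing data states that patients without post-treatment data "for any reason (loss to follow up, failure to complete treatment) will have their outcome multiply imputed under the assumption of missing at random (MAR"). It says that the models will use variables prognostic of outcome and others that predict missingness, and gives as examples "mean number of FI episodes per week at baseline, age, sex, and where available, mid-study bowel diary data". The imputation itself is then described as "using treatment allocation, patient sex and allocation as auxiliary variables". Allocation appears twice there and age not at all, which looks like a drafting slip and is a separate matter.

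The appendix table of imputation variables gives the same auxiliary set in every visible row: "Age, Sex and random allocation". Its introduction adds: "Baseline measures, mid-treatment (bowel diary data only) and end of treatment outcomes will be included together in the multivariate response". Centre is the only second-level variable.

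Four other statements bear on the point:

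- The analysis set is wide: "All patients randomised who receive the first treatment will be included in the intention-to-treat analysis of primary endpoint". A patient who stops after one session is therefore included.
- The only interim outcome is the mid-treatment diary (Follow up): "Week 7: bowel diary over 7 consecutive days".
- CRF5 is completed at the treatment visits, and under the comparison of compliance, "The distribution of the proportion of treatment sessions attended per patient will be compared descriptively by arm". A completer is someone with at least 10 sessions in 13 weeks.
- Sensitivity analyses for the primary outcome are marked not applicable.

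**The concern.** Missing at random is an assumption about what remains unexplained after conditioning on the variables in the model. The SAP itself links missing outcomes to patients not finishing treatment. Sessions attended measures that cause directly and may also predict outcome, yet it is left out.

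For a patient who stops after one or two sessions and has no week-7 diary, the model knows baseline values, age, sex, centre and arm. It cannot tell this patient apart from someone in the same arm who attended all 12 sessions. If stoppers respond less well, the imputed values are too favourable. In the PTNS arm that would raise the responder rate on which the primary comparison rests.

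**Working it through.** **1. What the models contain.** The body text names baseline outcome, age, sex, allocation and, where available, the mid-study diary. The appendix rows contain outcome measures, age, sex and allocation, with a random intercept for centre. No row lists sessions attended, time of stopping or completer status. The rows for patient-centred outcomes, SF-36, FI-QOL and EQ-5D also contain no FI episode count. Since only the diary was repeated mid-treatment, those rows carry no interim information even for patients who stop after week 7.

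**2. The plan's own figures.** The response rates of 55% (PTNS) and 35% (sham) come from the sample size section. A two-sided 5% test with 80% power needs 96 per arm without continuity correction and 106 per arm with it. The latter gives the stated 212. The rates are therefore used as printed, and nothing in this point changes the sample size.

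**3. Assumptions, because the SAP gives no figures.** Let *s* be the share of the PTNS arm that stops early, taken as 5%, 10% and 15%. Response is 55% in completers and *q* = 35% in stoppers. The final diary is missing for 2% of completers and 60% of stoppers, regardless of response within each group. Other covariates are ignored.

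**4. Formulas.**

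- True PTNS rate = 0.55(1 − s) + q·s
- Share of stoppers among observed patients: w = 0.40s / [0.98(1 − s) + 0.40s]
- Rate after imputation without exposure = 0.55(1 − w) + q·w
- Overstatement = (0.55 − q)(s − w)

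| s | True rate | w | Imputed rate | Overstatement |
|---|---|---|---|---|
| 5% | 54.0% | 0.020/0.951 = 2.10% | 54.6% | 0.20 × 2.90 = 0.6 points |
| 10% | 53.0% | 0.040/0.922 = 4.34% | 54.1% | 0.20 × 5.66 = 1.1 points |
| 15% | 52.0% | 0.060/0.893 = 6.72% | 53.7% | 0.20 × 8.28 = 1.7 points |

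Under the same assumptions, imputing separately for stoppers and completers recovers the true rate.

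**5. How far the result moves.**

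- Stoppers respond at 20%: 0.35(s − w) = 1.0, 2.0 and 2.9 points.
- Stoppers respond at 55%: zero.
- Stoppers respond at 65%: −0.10(s − w) = −0.3, −0.6 and −0.8 points, so the sign reverses.
- Every stopper lacks the final diary (w = 0) and *q* = 35%: 0.20s = 1.0, 2.0 and 3.0 points.

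**6. Effect on the contrast.** Take equal stopping and missingness in both arms.

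- If sham stoppers respond at 35%, like sham completers, the sham rate is unbiased and the contrast carries the full 0.6, 1.1 or 1.7 points.
- If sham stoppers respond at 15%, also 20 points below their completers, both arms are overstated equally and the difference is unbiased.

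**7. Scale.** With 227 randomised, about 113 per arm, the standard error of the difference is √[(0.55×0.45 + 0.35×0.65)/113] = √(0.475/113) = 6.5 points. The 1.1-point case is 1.1/6.5 = 0.17 of a standard error, or 0.011 × 113 ≈ 1 patient.

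**The case against.** A reader might infer that the plan overstates PTNS response, or that it gives early stoppers the result of a full course. The document supports neither. It reports no number of stoppers and no outcome for them, so the direction is unknown. The model learns from all observed patients in the arm, including partial-course patients who returned a final diary (40% of stoppers under the assumptions above). For diary outcomes, the week-7 diary can carry interim response for those who stop later. Patients who stop because they feel no benefit may do so in both arms, and the error then partly or wholly cancels.

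The row that matters most may also be out of sight. The amendments to version 1.0 say that the listing was updated to include the imputation model for the four binary outcomes, which include the primary outcome, but the table as it can be read has no such row. It may have been lost when the file was converted, so its content cannot be checked and is not criticised here. The examples in the missing-data section are also introduced as examples, which leaves that list open.

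Finally, the remedy has limited data to work with. At 10% stopping there are about 11 PTNS stoppers, of whom 0.40 × 11.3 ≈ 4 or 5 would have final diaries to inform about 7 without. At 5% stopping about 2 would. If no stopper has a final diary, the data hold nothing on stoppers' final outcomes.

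All of this stands, and it limits the claim. It does not explain why a predictor that the SAP ties to missingness, and already tabulates, is absent from every model that can be read. Imputing under missing at random from baseline and interim outcomes is conventional; adding attendance makes the assumption easier to defend.

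**Conclusion.** The point holds as a conditional one of minor weight. No visible imputation model includes treatment received, although the SAP gives non-completion as a cause of missing outcomes. PTNS response can be overstated by about 0.6 to 1.7 points at 5% to 15% stopping, if stoppers respond at 35% against 55% and lack the final diary in 60% against 2% of cases. All of these except the 55% and 35% are assumptions, and using 35% for stoppers is one too. The bias is zero if stoppers do as well as comparable observed patients, reverses if they do better, and cancels in the contrast if sham stoppers fall short by the same amount. Against a standard error of about 6.5 points it is small, and it does not show that the primary comparison is tilted towards PTNS.

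**What to change.** Add the number of sessions attended, or the SAP's own indicator of at least 10 sessions, as an auxiliary variable in each row of the appendix table and in the imputation model for the binary outcomes. State the same list in the missing-data section. Include an interaction with allocation, or impute by arm, only if enough early stoppers have observed final diaries to estimate it. Using a variable measured after randomisation is acceptable in an imputation model, and the plan already does so with the mid-treatment diary.

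The cost is a change of wording and one more covariate from data that the SAP already plans to summarise. The downside is slightly less precise imputation when few stoppers have final diaries. If the change is made after unblinding, it should be labelled as unplanned, as the SAP's introduction requires.
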